5.3.6.2 AE Analysis

All AEs and complications occurring from the time of subject enrollment until study termination or study completion including intra-operative AEs and complications, will be summarized by coded term, and by action taken.

An overall summary table of AEs, ADEs, SAEs, SADEs, USADEs, ASADEs, AEs leading to death, AEs leading to permanent impairment, removal/revision, DD, device failure and participation discontinuation will be presented. For each AE, the percentage of subjects who experience ≥ 1 occurrence of the given event will be summarized. The same summary will be provided for SAEs, SADEs, USADEs, ASADEs, as well as AEs leading to death, a permanent impairment of a body structure or body function, removal/revision, DD, device failure or study participation discontinuation.

AE summaries will be ordered in terms of decreasing frequency, and then alphabetically for the coded terms by Nonoperative Site Systemic Codes, or Operative Site Codes and associated sub-categories (if provided).

For each subject and each AE, the worst severity recorded will be attributed and used in the by-severity summaries. Similarly, the worst causality (most related to IP or the procedure) will be attributed and used in the by-causality summaries. As an exception, AEs that have missing causality (after data querying) will be assumed to be related to study drug.

By-subject listing of all AEs will be provided. The listings will include: subject identifier, adverse event (coded term), Nonoperative or Operative Site Codes and associated sub-categories (if provided), start/end dates and corresponding study day, relatedness to IP or procedure, seriousness, anticipated or not, leading to death, removal/revision or DD, leading to study participation discontinuation and other information. Additional summaries or listings may be provided, as appropriate.

Implant status collected will also be summarized by scheduled visit.

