### **4.3 STUDY PURPOSE**

This is a retrospective study to evaluate intra-operative, 6 months and 12 months safety and performance of the MINITAC◇ Ti 2.0 Suture Anchors for extremities repair to meet post-market clinical follow-up requirements as outlined by the Notified Body (BSI).

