### 7.4 SCREENING

Subject screening will include a retrospective chart review. To eliminate the potential for selection bias, Investigators will consecutively screen subjects that have undergone extremities repair using the MINITAC◇ Ti 2.0 Suture Anchor by date of surgery, starting from the earliest surgery date, moving forward in time, up until dates of surgery which are at least 12 months prior to the study start date at each site.

Participating study sites are required to document all screened subjects considered for inclusion in this study on the Screening and Enrollment Log. If a subject is excluded from the study, the reasons for exclusion will be documented on the Screening and Enrollment Log.

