### 7.5 INFORMED CONSENT

Study sites will obtain HREC/EC approval before any study specific activities are performed. The Investigator and the Participating Site shall treat all information and data relating to the Study disclosed to Participating Site and/or Investigator in this Study as confidential and shall not disclose such information to any third parties or use such information for any purpose other than the performance of the Study. The collection, processing and disclosure of personal data, such as patient health and medical information is subject to compliance with applicable personal data protection and the processing of personal data (16,17, 24).

Due to the retrospective nature of the study, a HREC/EC waiver of informed consent for study participation should be requested for those subjects who meet eligibility criteria. If allowed, the retrospective data set will be collected for these subjects. No prospective visits will be performed. In Australia, a waiver or alteration of the requirements for obtaining informed consent may be

Study Protocol—Device	
Safety and Performance of MINITAC® Ti 2.0 Suture Anchor in Extremities	Number: MINI.PMCF.2018.11
	Version: 3.0, 20Aug19
	Page: Page 18 of 56

granted by the HREC/EC under any of the following provisions set forth by the National Statement on Ethical Conduct in Human Research published by National Health and Medical Research Council, Australia (14):

- a) involvement in the research carries no more than low risk to participants
- b) the benefits from the research justify any risks of harm associated with not seeking consent
- c) it is impracticable to obtain consent
- d) there is no known or likely reason for thinking that participants would not have consented if they had been asked
- e) there is sufficient protection of their privacy
- f) there is an adequate plan to protect the confidentiality of data
- g) in case the results have significance for the participants' welfare there is, where practicable, a plan for making information arising from the research available to them
- h) the possibility of commercial exploitation of derivatives of the data or tissue will not deprive the participants of any financial benefits to which they would be entitled
- i) the waiver is not prohibited by State, federal, or international law.

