2 STUDY OBJECTIVES

2.1 Primary Objective(s)

The primary objective of this study is to assess safety and performance of the MINITAC[◇] Ti 2.0 Suture Anchor in extremities over a time period of 6 months after intervention.

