2.2 Secondary Objective(s)

The secondary objective of this study is to assess safety and performance of the MINITAC[◇] Ti 2.0 Suture Anchor in extremities over a time period of 12 months after intervention.

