3.5.3.2 Safety Endpoints

Safety endpoints include the collection of the following events from the subjects' medical record:

- All adverse events (AEs) and complications occurring from the time of subject enrollment until study termination or study completion including intra-operative adverse events and complications
- Device related re-intervention
- Device deficiencies (DDs)

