5.3 Statistical methods

5.3.1 General Analysis Definitions

Screening / Enrollment: For screening, only information available in the medical records will be reviewed. When all inclusion criteria and none of the exclusion criteria have been met for a subject and the informed consent process has been completed or a waiver of consent has been granted by the HREC/EC, the subject will be considered enrolled.

Baseline: Unless specified otherwise, the last non-missing value before study product installation/operation collected at the screening visit is considered as the baseline value.

Study Day:

Study Day = assessment date – study product installation/operation date + 1 for assessments post operation;

Study Day = assessment date – study product installation/operation date for assessments prior to operation;

All durations are calculated as the stop date minus the start date +1 unless otherwise specified.

End of Study: Due to the retrospective design of the study, end of the study is defined as the date when the last subject is documented on CRFs.

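### The only analysis set is limited to arthroscopic repairs although eligibility is not; and the stated adverse-event period starts at enrolment, more than 12 months after surgery

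*SAP*

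**What the plan says.** **Analysis set.** SAP 3.2.1 defines the FAS as enrolled subjects whose earlier repair with the anchor was *arthroscopic*, and uses it for all measures and endpoints. SAP 5.8 drops the protocol's separate safety and per-protocol sets in favour of the FAS alone, and SAP 5.3.6 applies it to safety. The Safety Population in protocol 10.2 carries the same word. Inclusion criterion 1 (protocol 7.2) asks only for an extremities repair with the device. SAP 5.3.3 and 5.5 still refer to a safety population that SAP 5.8 has abolished.

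**AE period.** SAP 5.3.6.2 summarises "All AEs and complications occurring from the time of subject enrollment until study termination or study completion including intra-operative AEs and complications". The endpoint definition in SAP 3.5.3.2 has the same span, "complications occurring from the time of subject enrollment until study termination or study completion", and so do the protocol synopsis and protocol 8.2.3. A subject joins once eligibility is met and (SAP 5.3.1) "the informed consent process has been completed or a waiver of consent has been granted by the HREC/EC, the subject will be considered enrolled". Protocol 7.2 requires more than 12 months since surgery, protocol 7.4 screens "up until dates of surgery which are at least 12 months prior to the study start date at each site", and protocol 7.5 adds: "No prospective visits will be performed". The objectives are safety and performance "over a time period of 6 months after intervention" (SAP 2.1) and "over a time period of 12 months after intervention" (SAP 2.2). Protocol 4.3 gives the purpose as "to evaluate intra-operative, 6 months and 12 months safety and performance of the" anchor.

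**AE collection.** Protocol 9.1.3 and 9.1.4 collect AEs and device deficiencies from discharge to the 6-month follow-up, and from there to the 12-month follow-up. Protocol 9.1.2 asks for them from enrolment to discharge, plus intra-operative complications. Protocol 12.3 requires AEs of any kind found in the source notes to be recorded.

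**The concern.** An analysis set that is narrower than the eligibility criteria removes people after they have been enrolled. With only one set and no sensitivity analysis (SAP 5.3.4), no other planned estimate would show the effect. The FAS is the denominator of the 6-month success rate, so a single word could decide who counts in the primary result.

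The AE rule reads as if carried over from a prospective study. In a chart review of patients already more than a year past surgery, a period that starts at enrolment covers the operation, through the added intra-operative clause, and then nothing until after month 12. That gap is the period in which the study says it will assess safety.

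**Working it through.** **1. The plan's own figure.** The only design figure nearby is the precision statement (SAP 5.7, protocol 11): 55.4% at 30 subjects and 98.8% at 50, for a 95% success rate. It reproduces as the binomial probability that the two-sided Clopper-Pearson 95% interval has half-width at most 10%:

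- N = 30: this allows at most 1 failure. P = 0.95^30 + 30 × 0.05 × 0.95^29 = 0.2146 + 0.3389 = 0.5535, against 55.4% stated.
- N = 50: this allows at most 6 failures. P = 0.9882, against 98.8% stated.

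The point here does not rest on these figures. They matter only because they count *enrolled* subjects, whereas the analysis would count FAS subjects.

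**2. Analysis set against eligibility.**

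| Source | Technique restriction |
|---|---|
| Protocol 7.2, criterion 1 | none: any extremities repair with the device |
| Protocol 6.1, indications | none listed |
| Protocol 6.5 | none beyond standard of care and the IFU |
| Protocol 8.3.2 | none: aims for the widest applicable population |
| SAP 5.5 | none: type of surgery and surgical technique are summarised as variables |
| Protocol 10.2, SAP 3.2.1 | arthroscopic only |

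Outside the reference list, the word occurs only in those two population definitions. SAP 5.8 lists the move to one set but does not mention or justify the restriction.

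Size: let *a* be the share of enrolled repairs that were arthroscopic. The literal FAS holds *a* × N subjects. The documents do not give *a*, so over its full range of 0 to 100% the FAS could hold 0 to 30 subjects at N = 30, or 0 to 50 at N = 50. At minimum enrolment, any *a* below 100% leaves fewer analysed than the 30 behind the 55.4%.

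**3. AE period against enrolment.** Count days from surgery and take 12 months as 365 days, as the protocol schedule does.

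- Earliest possible enrolment: day 366 (more than 12 months).
- Stated period: intra-operative events, plus enrolment to end of study.
- Overlap with post-operative days 1 to 365: none, for every eligible subject.
- Protocol 9.1.2, enrolment to discharge: the interval would start on day 366 or later and end at discharge from the index operation, so it runs backwards. It governs both AEs and device deficiencies.

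**4. A precedent in the SAP.** Protocol 9.1.5 records concomitant medication from enrolment. SAP 5.3.6.5 re-anchors it, running from the operation to the 12-month visit. The AE rule did not get the same correction.

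**The case against.** The strongest reply concerns the AE rule. Its intent is plain: the sentence includes intra-operative events, so enrolment cannot be a real cut-off. AE review is scheduled at all three chart reviews, protocol 9.1.3, 9.1.4 and 12.3 bring the AEs into the CRF, the by-subject listing is of all AEs, and study day runs from the operation (SAP 5.3.1). No passage tells a programmer to filter by enrolment date. This stands as far as it goes. It reduces the AE point to a contradiction between rules, but the only AE period that the SAP states is still the wrong one.

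A reader might infer more, in four ways that the documents do not support:

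- *That AEs in the first year are lost.* They are collected; only the stated analysis period omits them.
- *That the loss can be expressed as the overlap between the AE period and the 6- and 12-month review windows.* Those windows are tolerances for the timing of a review, while AE collection is continuous from discharge. Such a percentage says nothing about AE capture.
- *That the AE wording contaminates the primary endpoint.* Clinical success requires no device-related AEs, but SAP 5.3.2 takes this from items on the CRF status form and not from the period in SAP 5.3.6.2.
- *That non-arthroscopic subjects would vanish from every output.* Disposition (SAP 5.4.1) reports total enrolled, and the deviation summary (SAP 5.4.2) uses enrolled subjects. The exclusion applies to the endpoint and safety analyses.

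On the analysis set there is no comparable answer. It is fair to say that every enrolled repair may turn out to be arthroscopic, in which case nothing changes.

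**Conclusion.** Both conflicts are in the text and should be fixed before database lock. The analysis set is the main one: as written, it drops eligible, enrolled subjects from the denominator of the primary and all other endpoint and safety analyses, for a reason that appears nowhere in the eligibility criteria. Its size cannot be given, because no share of non-arthroscopic repairs is stated; the number could be zero, and the direction of any bias is unknown.

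The AE point is lesser. Read literally, the stated period covers none of the first 365 post-operative days apart from intra-operative events, which conflicts with the objectives and with the plan's own collection rules. This rests on enrolment as defined in SAP 5.3.1 and on 12 months being 365 days. It describes the rule and is not an estimate of missing AEs.

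**What to change.** **Analysis set.** Define the FAS as all enrolled subjects who had an extremities repair with the device, matching criterion 1. If the arthroscopic restriction is intended, reconcile it with the eligibility criteria and the sample size. Replace the leftover safety-population label in SAP 5.3.3 and 5.5 with FAS. Record this in SAP 5.8.

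**AE period.** In SAP 3.5.3.2 and 5.3.6.2, start the period at the index operation and keep in the tables all recorded AEs through the last available chart documentation. Summarise by onset within 182 and 365 days of the operation, whatever the review date. End each subject's follow-up at the last documented assessment if that is earlier, and show later AEs separately. Cutting at the reviews themselves would not do: the 6-month review may fall on day 182 − 150 = 32 and the 12-month review on day 365 − 150 = 215, or either may be absent. Say how the limits map to study day; under SAP 5.3.1, 182 and 365 days after the operation are study days 183 and 366. Record the change in SAP 5.8.

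**Protocol.** Correct the backward interval in 9.1.2, for AEs and device deficiencies, by clarification or at the next amendment. Protocol 10 lets the SAP document changes to the projected analyses, so the remaining points need not wait for an amendment.

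**Cost.** Text edits and slightly more tabulation, with no new data. If 9.1.2 is changed by amendment, signatory and HREC/EC approval is needed (protocol 15).

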## **5. OBJECTIVE(S)**

### **5.1 PRIMARY OBJECTIVE**

The primary objective of this study is to assess safety and performance of the MINITAC◇ Ti 2.0 Suture Anchor in extremities over a time period of 6 months after intervention.

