**9.1.3 Retrospective chart review at 6 Months (182 days) Post-Operative (+ 30 days / - 150 days)**

Given the retrospective study design, data will be collected from the medical chart to the extent it is available.

- |   |
|---|
| 
1. Collect the following retrospective data, to the extent it is available, from the subject's medical chart and complete the associated CRFs:
 
 
• Review study implant status 6 months post-operative for device related re-interventions and/or repair failure and assess clinical success.
 
• Obtain surgeon reported outcomes as defined in section 8.2.3 to the extent available at the 6 months follow-up.
 
• Collect Adverse Events and Device Deficiencies occurring from discharge until 6 months follow-up.
 
• Collect concomitant medications or therapies.
 
 |
|---|

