**9.1.4 Retrospective chart review at 12 Months (365 days) Post-Operative (+ 30 days / -150)**

Given the retrospective study design, data will be collected from the medical chart to the extent it is available.

- |   |
|---|
| 
1. Collect the following retrospective data, to the extent it is available, from the subject's medical chart and complete the associated CRFs:
 
 
• Review study implant status 12 months post-operative for device related re-interventions and/or repair failure and assess clinical success.
 
• Obtain surgeon reported outcomes as defined in section 8.2.3 to the extent available at the 12 months follow-up.
 
• Collect Adverse Events and Device Deficiencies occurring from 6 months until 12 months follow-up.
 
• Collect concomitant medications or therapies.
 
 |
|---|

Study Protocol—Device	
Safety and Performance of MINITAC® Ti 2.0 Suture Anchor in Extremities	Number: MINI.PMCF.2018.11
	Version: 3.0, 20Aug19
	Page: Page 27 of 56

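### The adverse event tables have no 6-month or 12-month cut, so overall AE and SAE incidence over the primary 6-month safety horizon is not tabulated

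*SAP*

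**What the plan says.** Protocol 5.1 and SAP 2.1 set the primary objective as safety and performance "over a time period of 6 months after intervention". Protocol 5.2 and SAP 2.2 set the secondary objective as the same thing "over a time period of 12 months after intervention".

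SAP 5.3.6.2 gives the period for the AE summaries, which starts at enrolment and runs as follows: "until study termination or study completion including intra-operative AEs and complications, will be summarized by coded term, and by action taken". The tables under that rule are an overall summary and breakdowns by coded term, action taken, severity and causality, based on the percentage of subjects with at least one event. The Protocol synopsis, Protocol 8.2.3 and SAP 3.5.3.2 use the same end point for collection. Protocol 10.5 asks for incidence as N (%) and adds no time cut.

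The collection steps are worded differently. Protocol 9.1.2 covers the period up to discharge. Protocol 9.1.3 then says: "Collect Adverse Events and Device Deficiencies occurring from discharge until 6 months follow-up". Protocol 9.1.4 says: "Collect Adverse Events and Device Deficiencies occurring from 6 months until 12 months follow-up". The schedule (synopsis and Table 9.1-1) has no later chart review and marks End of Study in the 12-month column. In SAP 5.3.1, however, "end of the study is defined as the date when the last subject is documented on CRFs", which is a calendar date for the whole study.

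**The concern.** A safety objective with a stated horizon calls for a table of events up to that horizon. Here the main safety tables give a single figure over a period whose end is not expressed as time since operation. If the plan is followed exactly, the report will not say what proportion of subjects had any AE, or any SAE, within 6 months, although that is part of the primary objective. The one percentage it does give could be taken as a 12-month risk, but only by a reader who assumes that collection stopped at the 12-month review at every site.

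**Working it through.** The plan's own computed figures, the precision probabilities of 55.4% and 98.8%, do not enter this point. The check compares planned outputs with objectives, plus window arithmetic.

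**1. Which safety outputs are tied to 6 and 12 months?**

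| Output | Where | At 6 months | At 12 months |
|---|---|---|---|
| Clinical success (requires no device-related AE, device deficiency, failure or re-intervention, among other items) | SAP 5.3.2, 5.3.3 | yes | yes |
| Incidence rate of device failure and/or device-related re-intervention | SAP 5.3.2, 5.3.3 | yes | yes |
| Re-interventions, device deficiencies, implant status | SAP 5.3.6.2 to 5.3.6.4 | by visit | by visit |
| AE, ADE, SAE and SADE tables | SAP 5.3.6.2 | no | not stated |

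The first three rows concern the device. An SAE unrelated to the device appears only in the last row. Clinical success is a composite, so a device-related AE lowers it without yielding an AE rate.

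**2. Windows** (SAP 5.3.2 and 5.3.3)

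- 6-month visit: 182 − 150 = day 32 to 182 + 30 = day 212.
- 12-month visit: 365 − 150 = day 215 to 365 + 30 = day 395.

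**3. Can the collection intervals stand in for a 6-month cut?** Not reliably. The first interval ends at the 6-month follow-up, which may fall on day 32 for one subject and day 212 for another. An event on day 100 then belongs to the second interval for the first subject and to the first interval for the second. Only onset counted from the operation gives the same horizon for everyone. SAP 5.3.1 defines study day, and the AE listing in SAP 5.3.6.2 already carries it.

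**4. Where does the AE period end?**

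- Collection steps and schedule: the 12-month review, so day 395 at the latest.
- Endpoint and table wording: study termination or completion, with no post-operative time attached.

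No section says which governs. By contrast, SAP 5.3.6.5 classifies medications as concomitant over a window from operation to the 12-month visit. AEs have no equivalent.

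**5. Size, as illustration only.** Assume that 10% of subjects have a first event within 12 months; the documents give no such rate. At constant risk, the 6-month figure is 1 − (1 − 0.10)^0.5 = 5.1%. If every first event fell in the first 6 months, it would be 10%. Under constant or falling risk, a 12-month figure of 10% is therefore compatible with a 6-month figure anywhere from 5.1% to 10%, and the planned tables cannot show where in that range it lies.

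**The case against.** Safety at 6 and 12 months is not absent from the plan. Clinical success excludes subjects with device-related AEs or device deficiencies, failure and re-intervention rates are planned at both times, and SAP 5.3.3 adds a Kaplan-Meier analysis of time to first failure or re-intervention. The AE listing gives dates and study day for at most 50 subjects, so a reader could count 6-month events by hand, and SAP 5.3.6.2 allows additional summaries. Scheduled collection ends at the 12-month review, so the cumulative table should be close to a 12-month table. All of this stands. It narrows the gap to overall AE and SAE incidence, but a count that can be made from a listing is not a planned result.

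A reader might also infer that AE percentages will mix follow-up of many years, because screening runs "starting from the earliest surgery date, moving forward in time" and the end of the study is a calendar date. The documents do not support that. They do not equate study completion in the AE rule with the calendar end of study, Protocol 12.4 uses completion at subject level, and no chart review is scheduled after 12 months. The wording leaves the end open; it does not show that years of later events will be collected.

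A fair objection to the remedy is that cuts at days 182 and 365 differ from the clinical success windows, which reach days 212 and 395, and that a cut alone does not cure incomplete charts. Both points are met by stating them with the table.

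**Conclusion.** The AE, ADE, SAE and SADE tables have no cut at either objective's horizon. Overall AE and SAE incidence over 6 months is not a planned output, and the 12-month end has to be inferred from the collection steps against differing endpoint wording. This should be corrected, and at low cost; it does not undermine the study. A reader might conclude that neither safety objective is answered, or that no 6-month safety figure will exist. That goes too far, since device-related components are reported at both times and the cumulative table approximates 12 months if the collection steps govern.

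The gap itself rests on the text alone. Its numerical effect cannot be derived from the documents; the range of 5.1% to 10% depends on the assumed 12-month rate and on constant or falling risk.

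**What to change.** In SAP 5.3.6.2, present the overall AE/ADE/SAE/SADE table cumulatively by onset in two columns: operation to 6 months (day 182) and operation to 12 months (day 365).

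- Say whether the cuts count days after operation or Study Day. Under SAP 5.3.1, 182 days after operation is Study Day 182 + 1 = 183.
- For each cut, state how many subjects have chart records reaching it. Charts are reviewed only as far as available, and SAP 5.6 imputes nothing.
- Add a footnote that the clinical success windows extend to days 212 and 395.
- Reconcile the collection-end wording in the Protocol synopsis, Protocol 8.2.3, SAP 3.5.3.2 and SAP 5.3.6.2 with Protocol 9.1.4, and list any later events separately. The enrolment start in the same sentences should be read again at that time, since the columns proposed here start at operation.

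Cost: SAP wording and one extra column per table, from dates already planned. Events after 12 months would appear only in a listing. The table change fits Protocol 10.5, which leaves additional safety summaries to the SAP. Aligning the Protocol text is an amendment that needs ethics committee approval under Protocol section 15.
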